## Study Intervention

This study is evaluating whether a 10mg intraosseous injection of morphine will help reduce inflammatory markers following surgery as well as reduce pain and pain medication use in patients undergoing primary total knee arthroplasty when compared with patients receiving the current standard of care for primary total knee arthroplasty. In the post-operative period study patients will have their post-operative opioid consumptions monitored while in the hospital and for 14 days following their surgery. Study patients will not be allowed Ketorolac or Celecoxib (Toradol), both non-steroidal anti-inflammatories (NSAIDs), in the PACU / post-operative period following their total knee replacement. This is being done because the research team wishes to standardize the post-operative care protocols across all 3 providers participating in the study since not all prescribe NSAIDs in the post-operative period following TKA. Additionally, there is no method for NSAIDs like Ketorolac or Celecoxib to be converted into morphine equivalence scores and thus would prevent accurate quantification of pain relief provided in the post-operative period.

Should the patient suffer any side-effects from the IO morphine injection they will have all of the necessary care provided to them. This study will require the patient to consent to a number of study-related items including that do not fall under their usual standard of care:

- Filling out study surveys (PROMIS Global Health SF v1.1 and KOOS JR) at pre-op, 2 weeks post op, 8 weeks post op, and 1 year post-op. The surveys will be sent through RedCap.
- Blood draws to measure systemic levels of inflammatory cytokines right after induction of anesthesia, 15 minutes post tourniquet release, and 10 hours post op. This sample will be collected by a qualified Houston Methodist nurse or qualified member of the research team (ie physician/fellow/resident).

- Filling out a symptom journal for 2 weeks post op that will record pain, pain medication use, nausea (including emesis), and bowel movements.
- Lastly, patient range of motion will be recorded from their physical therapist' progress notes and at 2 week post-operative follow-up appointment.

This study will not require the patient to attend any additional study visits. The expected amount of time the patient for the patient to complete all study related items including filling out the symptom journal and answered pre/post-op surveys is approximately 90 minutes. The patient will participate in the study for a total of 52 weeks. The anticipated duration to enroll all study subjects is 18 months. The estimated date for the investigators to complete primary analyses is 2.5 years following the initiation of the study.

#### 4. Drugs, Biologics, Devices

Morphine is approved by the FDA and it will be administered intraosseously. This method of administration has been shown to provide a similar pharmacokinetic profile when compared to IV morphine. Intraosseous morphine injection in primary total knee arthroplasty is not considered standard of care as it is not known if it helps with post-operative pain.

The most serious side effects of morphine include respiratory depression, apnea, circulatory depression, respiratory arrest, shock, and cardiac arrest. More common adverse effects include sedation, lightheadedness, dizziness, nausea, vomiting, and constipation. Patients will be monitored in the post-operative period for these side effects prior to discharge.

#### 5. Data Privacy / Confidentiality

Houston Methodist policies for handling Protected Health Information will be followed including all requirements for physical and electronic data security, use of encrypted devices, and utilizing HM password protected servers. All data for this study will be complete, accurate, original, and legible. All physical study related data such as the symptom journal will be stored in a locked office cabinet of a qualified member of the research team. All electronic data such as the surveys sent from Houston Methodist's RedCap system (KOOS JR & PROMIS Global Health) will be password protected and only accessible by members of the research team. The data for this study will be maintained indefinitely. Any data that is published as a result of this study will be completely de-identified including the removal of any PHI.

The only PHI being used by the research team for this study are dates including discharge dates and birth date (to determine age at time of surgery) as well as MRNs. The use of identifiable data is necessary for the research team to confirm past medical history of morphine allergy, acute or chronic liver disease, or opioid addiction to ensure only qualified patients are recruited into the study. No PHI will ever be disclosed beyond Houston Methodist. This data will be stored along with other data recorded from Epic on password protected servers accessible only to qualified members of the research team.

Identifier (or parts of)	Recorded	Disclosed	Comment
Names	Yes	No	Recorded prior to any recruitment method (phone or email). Needed so that qualified members of the research team can properly address the patient over phone or email to inform them about the study.
All elements of dates (except year) for dates directly related to an individual, including birth date, admission date, discharge date, date of death; and all ages over 89 and elements of dates (including year) indicative of such age	Yes	No	Recording birth date to determine age at time of surgery. Recording surgery date as well as the discharge date.
Phone numbers; Fax numbers	Yes	No	For recruitment purposes. However the informed consent for this study will only take place in person with a qualified member of the research team. Also needed to remind a patient to bring their symptom journal to their standard 2 week post op appointment with [name], [name], or [name]..
Email address	Yes	No	Needed to email Houston Methodist RedCap surveys to study patients or remind a study patient to bring their symptom journal to their standard 2 week post op appointment with [name], [name], or [name].
Medical record numbers	Yes	No	Necessary to confirm past medical history.

## 6. Study Population

see pages 3-4 section 3 of this protocol.

Patients will be approached if they are undergoing TKA at Houston Methodist Hospital. Study coordinator, [name], or other qualified member of the research team (qualified to give informed consent) will determine if patients are eligible, and then consent the patient during their pre-operative visit.

## 7. Screening and Recruitment S R

The research team requests a waiver of authorization for preparatory for research. It would not be practical to conduct this research study without preliminary screening of potential study patients. Without the waiver the research team would have to request fan authorization to view PHI from every patient of [name], [name], and [name] to determine if they could be a possible candidate for the research study. There is no risk related to this waiver of authorization. Data safety practices of all PHI have been described in the section 6 on page 6 of this protocol.

Potential study patients will be identified by the research team prior to their surgery date by looking at [name], [name], and [name] surgery schedule searching for primary total knee arthroplasty surgeries. The potential study patient's medical records will then be viewed in Epic to identify and confirm inclusion and exclusion criteria including morphine allergy, pregnancy status, past medical history, type of surgery, weight, and BMI. If the patient meets the initial criteria to participate in the study then a qualified member of the research team will email or call the patient to inform them about the study and determine if they are interested in possibly participating. Alternatively, the recruitment process may also take place at in clinic ([name] or at the Houston Methodist Pin Oak [name]) after the patient's visit with [name], [name], or [name]. In either scenario, meaning phone/email/or in person recruitment, potential study patients will be screened for inclusion and exclusion criteria prior to the informed consent. The informed consent will take place in person with a qualified member of the research team where the patient will be informed about all aspects of the research study to determine if they wish to participate. The screening document as well as the email/telephone call recruitment templates will be included in the IRB application.

Sensitive information such as history of morphine addiction will be asked during the screening process. Should a patient admit to that history and consequently be excluded from the study the screening document will immediately be disposed of in a HIPAA bin to later be shredded. Any data from that patient prior to inclusion in the study will be deleted except for their name and "EXCLUDED FROM PARTICIPATION" in the dataset. It is important to note that screening data will not be collected from email and will only be done either in person or over the phone.

## 8. Withdrawal of Subjects

Patients may be withdrawn from the study if it is discovered that they have any of the exclusion criteria that was not previously identified during the recruitment and screening process. If this is the case the patient will be informed of their removal from the study and the reason why they were removed from the study.

If a study patient has an allergic/negative reaction to the IO morphine injection that the event will be reported immediately to the IRB and the patient will be removed from the study.

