## 3. Study Design

This study is a double-blind randomized controlled trial with two arms. The control group will receive an intraosseous (IO) injection of antibiotics as per [name], [name], and [name] standard of care for primary TKA patients. The experimental group will receive an IO injection of antibiotics mixed with 10 mg of morphine. A research coordinator on the study team will inform the circulator nurse present in the OR during the study patient's case about which group (morphine or no morphine) the patient is in. The circulator nurse will then be instructed to place morphine into the surgical field during the mixing process of the intraosseous solution without notifying the surgeon to ensure the double blind. Patient's post-operative pain levels, pain medication consumption, side effects to pain medications, and range of motion will be recorded for 14 days following surgery.

Patient outcomes will also include pain levels, post-operative pain medication use, and post-operative ROM.

The anticipated total number of participants is 84 with 42 patients being in each group. The maximum number of subjects who will be enrolled is 84 patients (i.e. give consent to participate) at this site.

Participants will be randomized into either the control group or the experimental group by an excel-based software program.

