### **Exclusion criteria**

- Patient lacks the capacity to consent to the research project (study will not utilize LAR signatures during the informed consent process)
- Weigh < 100 pounds
- BMI > 38
- Pregnancy or suspected pregnancy
- Past medical history of opioid addiction.
- Established hypersensitivity (ie allergy) to morphine.
- Acute or chronic liver disease for example cirrhosis.
- Use of any narcotics 5 days before surgery (opioids, hydrocodone, morphine, hydromorphone, fentanyl, etc).
- Undergoing bilateral total knee replacement, revision total knee arthroplasty, or any additional procedure outside of a primary total knee arthroplasty.
- Unable to get general and spinal anesthesia.
- Same-day discharge on day of surgery.

We will access the following data from medical records (Epic) including PHI:

- MRN, date of surgery, age, gender, past medical history, height, weight, BMI, laterality, pre-operative ROM, pre-operative pain VAS, intra-operative tourniquet pressure, procedure duration, and medications received during hospital stay.

Post-operatively we will ask study patients in both groups to complete a post-op symptom journal that will collect the following information in the interim before the patient's standard 2 week post op appointment with [name], [name], or [name]:

- Record daily pain levels using a validated pain scale for 14 days post op.
- Record daily pain medication use for days 14 post-op.
- Record daily nausea levels using a validated scale as well as recording bowel movements and any instances of emesis for 7 days post op.

Additionally, the tourniquet pressure intra-op will be standardized to 275 mmHg across all 3 providers on the research team (Drs. [name], [name], and [name]). This falls within the normal standard of care for all 3 providers for their total knee arthroplasty patients. However, it has been shown in the literature that tourniquet pressure can influence acute post-operative muscle quality including increased pro-inflammatory cytokines. Therefore, to limit outside factors on post-operative inflammatory marker levels as well as post-operative rehabilitative outcomes the research team will use the same tourniquet pressure for all study patients. This does not reflect an elevation in risk for study patients since 275 mmHg falls within range of standard of care for total knee arthroplasty patients for all 3 providers.

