### **Baseline and Post-op Blood Samples:**

Systemic sample – Blood draws will only be done with [name] patients that decide to participate in the study if they are the first or second case of the day. Three blood draws will be taken in these patients including just after induction of anesthesia, 15 minutes after the tourniquet is released, and 10 hours post op. The 10hr post-op blood draw timing will be based on the timing of the intraosseous injection. Serum samples will be used to measure inflammatory cytokines IL-6 and IL-8, and expression of CD11a, CD11b, CD11c, and CD18 as well as the systemic level of morphine present in the blood. Only these specific study patients will be having blood draws done due to the 10 hr post-op draw needing to be processed within 30 minutes of the draw. Blood samples will be collected in EDTA glass tubes by Houston Methodist nursing staff or a qualified member of the research team (eg. physician, fellow, or resident). Up to 10 ml of blood will be collected per time point.

For our primary outcome variable of VAS recorded pain, power analysis was performed using JMP statistics software utilizing data extracted from prior work done on the average VAS-Pain scores for TKA patients.

The statistical model for this investigation to be utilized in this investigation is a 2(Treatment) x 2(Time-point) mixed model analysis of covariance with repeated measures, co-varied on pre-operative VAS scores recorded on the day of surgery. Although there will be several days of VAS recorded out to 14-days post-surgery, the statistical question for pairwise comparisons will be to determine (1) how pain recorded on each subsequent day compares back to initial baseline (pre-operative) values within each group (treatment vs control) and (2) how each group compares to each other at the same measurement time-point. Therefore, each subsequent day will be modeled separately against the baseline value.

From the reference cited above, the 3-day average VAS score immediately following TKA was 3.2 cm (standard deviation, 2.0cm). The minimum detectable change (MDC) to detect will be set at 1.6cm as described in the literature.

The primary hypotheses of the study is that the treatment group will experience a reduction in post-operative pain compared to the control group. Based on the previous literature listed above, for a power analysis of 2 groups across 2 time-points, to detect a MDC of 1.6cm at a statistical

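### Section 8 removes patients who react to IO morphine without saying that follow-up and as-randomised analysis continue: a minor, cheaply closed route to selective data loss

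*Combined protocol and SAP*

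**What the plan says.** Section 8 (Withdrawal of Subjects) contains two rules. The first is discretionary and concerns eligibility problems found late: "Patients may be withdrawn from the study if it is discovered that they have any of the exclusion criteria that was not previously identified". The second is mandatory. Its trigger is "If a study patient has an allergic/negative reaction to the IO morphine injection", and its consequence is that "the event will be reported immediately to the IRB and the patient will be removed from the study". The section gives no definition, grade or time window for a negative reaction.

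Section 3 (Study Design) confines the study drug to one arm: "The experimental group will receive an IO injection of antibiotics mixed with 10 mg of morphine". Controls receive the IO antibiotics alone. Section 3 also plans that "side effects to pain medications, and range of motion will be recorded for 14 days following surgery", and the journal described after the exclusion criteria includes nausea scores and "recording bowel movements and any instances of emesis for 7 days post op". Under Study Intervention, surveys run to 1 year.

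The statistical plan, printed in Section 3 after the blood-sample text, specifies a "mixed model analysis of covariance with repeated measures, co-varied on pre-operative VAS scores recorded on the day of surgery" and adds that "each subsequent day will be modeled separately against the baseline value". It names no analysis population and no rule for missing data. It also stops recruitment if adverse effects differ significantly between the groups.

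**The concern.** IO morphine is given once, during surgery, so by the time anyone can react no study treatment is left to stop. What Section 8 ends is the patient's participation, not a course of drug. Because only one arm receives the drug, the trigger arises wholly or mainly in that arm.

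If removal also ends the journal, surveys, range-of-motion and chart data, the losses depend on response to the assigned treatment. Patients who react may differ in pain, opioid use and side effects from those who do not, and randomisation no longer balances the patients who remain. The roughly 20% dropout allowance covers the number lost, not which patients are lost.

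The analysis offers limited repair. Each post-operative day is compared with baseline in its own model, so a removed patient's earlier journal days do not inform the later days. The plan also leaves open whether a removed patient's reaction counts in the between-arm adverse-effect comparison.

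**Working it through.** **Inputs from the documents.** Target difference 1.6 cm, SD 2.0 cm, power 0.9, alpha 0.05 (sidedness not stated), 35 evaluable and 42 recruited per arm, 14 journal days, and under 1% for the most serious morphine risks (Section 3 and Section 10). The common effects are listed without frequencies.

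**Inputs that are assumptions.** The fraction q of the morphine arm removed (beyond the <1% figure), and the correlation r between tendency to react and post-operative pain.

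**1. The plan's sample size.** n = 2(1.960 + 1.282)² × 2.0² / 1.6² = 32.8, so 33 per arm. An exact two-sample t-test gives 34. The stated 35 is consistent, with power about 0.91.

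**2. Narrow reading (serious events only, q = 1%).** Expected removals are 42 × 0.01 = 0.42. The chance of none is 0.99^42 = 0.66. A patient removed before day 1 loses 14 of 42 × 14 = 588 planned morphine-arm daily pain records, or 2.4%.

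**3. Bias if removed patients give no later data.** Suppose the fraction q with the highest reaction tendency is removed from the morphine arm only. The retained mean then shifts by

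bias = SD × r × k(q), with k(q) = φ(z)/(1 − q) and z the (1 − q) normal quantile.

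| q | k(q) | r = 0.3 | r = 0.5 |
|---|---|---|---|
| 1% | 0.027 | 0.016 cm | 0.027 cm |
| 10% | 0.195 | 0.117 cm | 0.195 cm |
| 20% | 0.350 | 0.210 cm | 0.350 cm |

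Positive r favours morphine. At r = −0.3 the bias is 0.12–0.21 cm against morphine (q = 10–20%), and at r = 0 it is nil. To reach a tenth of the target (0.16 cm), q must be 7.9% at r = 0.5 (3.3 of 42 patients) or 14.5% at r = 0.3 (6.1 of 42).

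**4. Removals in the control arm.** If controls are removed at half the morphine rate, the bias falls to 0.117 − 0.065 = 0.052 cm (q = 10%, r = 0.3) or 0.350 − 0.195 = 0.155 cm (q = 20%, r = 0.5). At equal rates, with the same r, it is zero.

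**5. Baseline covariate.** Take an assumed correlation of 0.4 between baseline and post-operative pain. If reaction tendency is as closely related to baseline as to post-operative pain, 0.117 and 0.350 cm fall to 0.070 and 0.210 cm. If it is unrelated to baseline, adjustment changes nothing. If the link runs wholly through baseline, adjustment removes the bias.

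**6. Error rate with no true effect.** Simulating one post-operative day with baseline adjustment and random dropout from 42 to 35 in both arms, the two-sided 5% test rejects about 5.5–5.8% of the time at q = 10%, r = 0.3.

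A second method sets bias = q × d, where d is the excess mean pain of removed over retained patients. The table implies d of 1.2–2.0 cm at q = 10% (0.117/0.10 and 0.195/0.10) and 1.1–1.8 cm at q = 20%. With d of 1–2 cm, an unadjusted t-test starting from 42 per arm rejects 5.6–7.3% of the time at q = 10% and 7.1–13.7% at q = 20%.

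**7. Power.** Starting from 35 per arm, removing 10% or 20% of the morphine arm leaves power at 0.897 or 0.874. The issue is bias, not power.

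**The case against.** The strongest reply is that the rule was probably meant for notable events only. A negative reaction is paired with an allergic one and triggers an immediate report to the IRB. The protocol also plans to record nausea, emesis, bowel movements and side effects for 7 to 14 days, and removing patients for the events the journal exists to capture would defeat that plan. This stands as the more likely reading, and under it the effect is negligible. The text does not say so, however, and the common morphine effects are not excluded anywhere.

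The one-sided loss is also less certain than the wording suggests. The trial is double-blind, so staff may attribute a control patient's symptoms to IO morphine. The revision history records that morphine is allowed post-operatively, without distinguishing the arms, so morphine-type reactions can occur in controls. Both weaken the bias; neither guarantees equal removal rates.

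The consent pages were not available and may address data after withdrawal. Even so, the set of patients analysed belongs in the statistical plan.

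A reader might go further than the documents allow in three ways:

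- **That the trial will be materially biased towards morphine.** No documented rate supports the 10–20% scenarios, and the sign of r is unknown.
- **That the recruitment-stopping rule is emptied.** Section 8 has the event reported; what is unstated is only how it counts in the comparison.
- **That data already collected are discarded.** Section 5 keeps study data indefinitely. Section 10 speaks of deletion after the study is complete, in the context of tissue records. Neither says that a removed patient's earlier data are dropped.

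**Conclusion.** The gap in the text is certain: mandatory removal after randomisation and injection, an undefined trigger tied to one arm's treatment, and no visible statement on continued follow-up or analysis by assigned arm. Followed literally, it can lose later pain, opioid-use and safety data selectively.

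Its practical size is small on the evidence available. At the only documented rate, under 1%, the bias is at most about 0.03 cm of a 1.6 cm target (for r up to 0.5). A bias of 0.1–0.35 cm requires three assumptions together: that common effects count as negative reactions, that 10–20% of the morphine arm is removed while controls are not, and that reaction tendency correlates 0.3–0.5 with pain. The direction follows the sign of that correlation. These are illustrations, not predictions. The point is a minor correction, worth making because it costs almost nothing.

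**What to change.** In Section 8 and the statistical plan, state that:

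1. A reaction is reported to the IRB as planned, but journal, survey, range-of-motion and chart data collection continues unless the patient withdraws consent.
2. All randomised patients are analysed in their assigned arm, and every reaction counts in the between-arm adverse-effect comparison of Section 3.
3. A negative reaction, for reporting purposes, means a listed set of events.

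The cost is a few sentences, with no new visits or measurements and no change to the sample size. The downside is that a few atypically managed patients stay in the analysis. The change concerns data collection, reporting definitions and analysis only; it takes no position on how reactions are managed clinically.
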